2.2 Study Design

2.2.1 *Overview*

This study is a multisite, placebo-controlled, double-blind, randomized Phase 3 study in approximately 300 participants with a history of HeFH who are not adequately controlled by their lipid-modifying therapy to evaluate the efficacy, safety, and tolerability of obicetrapib.

Approximately 300 eligible participants will be randomized in a 2:1 ratio, respectively, to the

following treatment groups:

- Obicetrapib group: one 10 mg obicetrapib tablet once daily; or
- Placebo group: 1 placebo tablet once daily.

At least 70% of the participants enrolled into this study must be taking high intensity statins (HISs). HeFH diagnosis is defined by existing confirmation via genetic testing, WHO Criteria/Dutch Lipid Clinical Network (DLCN) Criteria with a score of >8 points, and/or Simon Broome Register Diagnostic Criteria [1,2].

Starting on Day 1, each participant will self-administer their assigned study drug once daily until Day 365. During the Treatment Period, participants will return to the study site for efficacy and safety assessments. Blood samples for pharmacokinetic (PK) assessment will be collected at specified visits throughout the study. The End Of Study (EOS) Visit will be conducted approximately 35 days after the participant's last dose of study drug, during which vital signs; limited serum chemistry, hematology, and coagulation parameters; pharmacokinetics; concomitant medications; and AEs will be assessed.

The study drug blind will be maintained through the EOS Visit (Visit 8). Participants, the Sponsor, Investigators, and all study site personnel involved in the study, including personnel carrying out study procedures, evaluating participants, entering study data, and/or evaluating study data, will remain blinded to treatment allocations until all participants have completed the EOS Visit assessments and the database has been locked for analysis.

Active and placebo products will be identical. Medication bottles with a unique code will be assigned to participants at various points in the study by the Medpace Interactive Response Technology system.

Refer to [Table 1 Schedule of Procedures](#) for a complete list of procedures to be completed at each study visit.

Table 1 Schedule of Procedures

Visit	Screening		Treatment Period					EOS
	V1	V2	V3	V4	V5	V6	V7/EOT/ET ¹	
Study Day	-14 to -1	1	30	84	180	270	365	35 days after last dose
Window (±days)	±3		±3	±7	±7	±7	±7	±7
Informed consent	X							
Assessment of eligibility	X ²	X ²						
Demographics and medical history	X							
Pregnancy test, FSH ³	X	X	X	X	X	X	X	
TSH	X							
Randomization		X						
Study drug administration		X	X	X	X	X	X	
Physical examination ⁴	X							X
Weight, height, and BMI	X ⁵							X
Vital signs ⁶	X	X	X	X	X	X	X	X
12-lead ECG ⁷		X						X
Lipid profile/biomarkers (fasting) ⁸	X	X	X	X	X	X	X	
Serum archive sample for future assessment of biomarkers related to dyslipidemia and/or CV risk (fasting) ^{8,9}			X					X
UACR, UPCR (fasting) ⁸		X	X	X	X	X	X	
Aldosterone, hsCRP (fasting) ⁸		X	X	X	X	X	X	
Lp(a), ApoA1(fasting) ^{8,9}	X	X		IX				
Full serum chemistry (fasting) ^{8,9}		X			X			X
Limited serum chemistry (fasting) ^{8,9}	X		X	X		X		X
Urinalysis (local) ¹⁰	X	X						X
Hematology and coagulation (fasting) ^{8,9}	X	X			X		X	X
PK sample (central) ^{9,11}		X		X ¹²	X		X	X
Prior/concomitant medications	X	X	X	X	X	X	X	X
Study drug dispensation		X	X	X	X	X		
Study drug return/compliance calculations			X	X	X	X		X
AEs assessment	X	X	X	X	X	X	X	X

1. For participants who permanently discontinue from study treatment **and who decline continued study participation**, an ET Visit will be scheduled as soon as possible followed by an onsite EOS Visit 35 days later. The ET Visit procedures are identical to the EOT Visit procedures. If the discontinuation occurs at a specific onsite visit, this visit will become the ET Visit and EOT Visit procedures should be followed. Participants who withdraw consent to all follow-up will be asked about the reason(s) and will be assessed for the presence of any AEs..

2. Assessment of laboratory eligibility criteria will be based on central laboratory values obtained within timeframes defined in the inclusion and exclusion criteria.

3. Urine pregnancy tests will be performed for females of childbearing potential only (performed locally using central laboratory kit supplies). FSH will only be performed at Screening in females <55 years of age and postmenopausal, defined as ≥1 year since their last menstrual period.

4. The physical examination should comprise a focused examination, which includes general, respiratory, CV, abdominal, and extremities evaluations; ophthalmological examination and recording of weight and height.
5. Height will be measured at Screening only and used to calculate BMI.
6. Vital signs (consisting of heart rate and blood pressure) will be measured as described in [Section 8.8](#).
7. A single 12-lead ECG will be performed in the supine position after 10 minutes of rest.
8. Participants must fast for a minimum of 8 hours prior to samples being collected.
9. Samples should be collected prior to study drug administration.
10. Urinalysis will be performed locally by dipstick analyses from a sample of mid-stream urine. In case of abnormal results, microscopy and other assessments will be performed at the local laboratory and the abnormality recorded as an AE.
11. A PK sample will be collected prior to study drug administration for trough measurement of obicetrapib in plasma. At Visits 2, 5, and 7, participants should take study drug after a trough PK sample has been drawn.
12. The PK sample at Visit 4 is not designated in the protocol, however the PK will be assessed using residual serum from the Day 84 limited chemistry panel to confirm patients are taking IP.

AE = adverse event; ApoA1 = apolipoprotein A1; BMI = body mass index; CV = cardiovascular; ECG = electrocardiogram; EOS = End of Study; EOT = End of Treatment; ET = Early Termination; FSH = follicle-stimulating hormone; hsCRP = high sensitivity C-reactive protein; Lp(a) = lipoprotein (a); PK = pharmacokinetic(s); TSH = thyroid-stimulating hormone; UACR = urine albumin-creatinine ratio; UPCR = urine protein-creatinine ratio; V = Visit.

2.2.2 *Sample Size Determination*

Enrollment of approximately 300 participants globally is planned for this study.

Assuming an approximate 5% drop out rate, approximately 285 participants will be evaluable for efficacy. This sample size of at least 285 evaluable participants will provide more than 90% power to detect a 30% reduction of LDL-C (standard deviation 15%) levels in the obicetrapib group compared to the placebo group at a 1-sided significance level of 0.025. This sample size will also contribute to sufficient participant exposure and safety data.

2.3 Study Endpoints

2.3.1 *Primary Efficacy Endpoints*

The primary efficacy endpoint is the percentage change from Baseline to Day 84 in LDL-C in the obicetrapib group compared to the placebo group.

2.3.2 *Secondary Efficacy Endpoints*

The secondary efficacy endpoints include the following:

- Percentage change from Baseline to Days 180 and 365 in LDL-C in the obicetrapib group compared to the placebo group;
- Percentage change from Baseline to Days 84, 180, and 365 in ApoB in the obicetrapib group compared to placebo group;
- Percentage change from Baseline to Days 84, 180, and 365 in non-HDL-C in the obicetrapib group compared to placebo group;
- Percentage change from Baseline to Days 84, 180, and 365 in HDL-C in the obicetrapib group compared to placebo group;
- Percentage change from Baseline to Days 84 and 365 in Lp(a) in the obicetrapib group compared to placebo group;
- Percentage change from Baseline to Days 84, 180, and 365 in TC in the obicetrapib group compared to placebo group;
- Percentage change from Baseline to Days 84, 180, and 365 in TG in the obicetrapib group compared to placebo group.

2.3.3 *Exploratory Efficacy Endpoints*

The exploratory efficacy endpoints include the following:

- Individual responsiveness defined as the number of participants reaching on treatment LDL-C levels of <40 mg/dL (<1.04 mmol/L), <55 mg/dL (<1.42 mmol/L), <70 mg/dL (1.81 mmol/L), and <100 mg/dL (<2.59 mmol/L) at Days 84 and 365;
- Individual responsiveness defined as the number of participants reaching on treatment non-HDL-C levels of <85 mg/dL (<2.20 mmol/L), <100 mg/dL (<2.59 mmol/L), and <130 mg/dL (<3.37 mmol/L) at Days 84 and 365;

- Individual responsiveness defined as the number of participants reaching on treatment ApoB levels of <65mg/dL (<0.65 mmol/L), <80 mg/dL (<0.80 mmol/L), and <130 mg/dL (<1.30 mmol/L) at Days 84 and 365;
- Percentage change from Baseline to Day 84 and 365 in ApoA1 in the obicetrapib group compared to the placebo group; and
- Trough levels of obicetrapib from Baseline to Days 84, 180 and 365 in the obicetrapib group;

2.3.4 Safety Endpoints

The safety endpoints include the following:

- Safety and tolerability profile of obicetrapib assessed by AEs, ESIs, vital signs (including blood pressure as assessed by office blood pressure measurements), ECG, and clinical laboratory values.

3 STATISTICAL METHODOLOGY

3.1 General Considerations

3.1.1 Analysis Day

Analysis day will be calculated from the date of first dose of study drug. The day of the first dose of study drug will be Day 1, and the day immediately before Day 1 will be Day -1. There will be no Day 0.

3.1.2 Analysis Visits

Scheduled visits will be assigned to analysis visits as recorded on the CRF.

For each analysis visit, if a scheduled visit occurs within the analysis day window, then the measurement from this scheduled visit will be used. If no scheduled visit occurs or laboratory results of the scheduled visit were unreportable, the unscheduled measurement closest to the target day will be used. If measurements are equidistant to the target day, the latter will be used. Otherwise, unscheduled visits will not be re-assigned and will remain labelled as unscheduled. If laboratory measurements for the scheduled visit were taken while a participant was not in a fasting state and laboratory measurements are available from an unscheduled visit during which the participant was in a fasting state (and the visit occurred within seven days of the scheduled visit), those fasted labs will be utilized in place of the unfasted labs.

Early termination (ET) visits will be assigned to analysis visits according to the following visit windows in Table 2:

Table 2 Analysis Visit Windows

Analysis Visit	Target Analysis Day	Low Analysis Day	High Analysis Day
Day 1 (Visit 2)	1	NA	NA
Day 30 (Visit 3)	30	2	57
Day 84 (Visit 4)	84	58	132
Day 180 (Visit 5)	180	133	225

Day 270 (Visit 6)	270	226	317
Day 365 (EOT)/(Visit 7)	365	318	N/A

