For participants who permanently discontinue from study treatment **and who decline continued study participation**, an Early Termination (ET) Visit will be scheduled as soon as possible followed by an EOS Visit approximately 35 days later. The ET Visit procedures are identical to the End of Treatment (EOT) Visit procedures. If the discontinuation occurs at a specific onsite visit, this visit will become the ET Visit and EOT Visit procedures should be followed. Participants who withdraw consent to all follow-up will be asked about the reason(s) and will be assessed for the presence of any AEs.

If premature withdrawal from the study occurs for any reason, the Investigator must determine the primary reason for a participant's premature withdrawal from the study and record this information in the medical records and on the electronic case report form (eCRF).

Withdrawn participants will not be replaced.

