5 STUDY TREATMENTS

5.1 Treatment Groups

Approximately 300 eligible participants will be randomized in a 2:1 ratio, respectively, to the following treatment groups:

- Obicetrapib group: One 10 mg obicetrapib tablet once daily; or
- Placebo group: 1 placebo tablet once daily.

All study drugs will be administered by the participant orally on Days 1 to 365.

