9.2.5 Sample Size Determination

Enrollment of approximately 300 participants globally is planned for this study.

Assuming an approximate 5% drop out rate, approximately 285 participants will be evaluable for efficacy. This sample size of at least 285 evaluable participants will provide more than 90% power to detect a 30% reduction of LDL-C (standard deviation 15%) levels in the obicetrapib group compared to the placebo group at a 1-sided significance level of 0.025. This sample size will also contribute to sufficient participant exposure and safety data.

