Missing data will be imputed for the primary efficacy analysis based on a pattern mixture model that uses a multiple imputation technique analyzed with ANCOVA with pre-specified fixed factors and covariates. If appropriate, based on the number of retrieved dropouts, missing measurements of non-retrieved dropouts will be modeled by known measurements from retrieved dropouts (ie, participants who remain in the study after treatment discontinuation) in the same treatment group. If the number of retrieved dropouts is such that the model convergence is questionable and the given parameter estimates cannot be obtained, then missing data at the Day 84 assessment will be estimated based on the placebo treatment group as described in subsequent sections of the SAP corresponding to the first sensitivity analysis.

Missing data at Day 84 will be imputed using a retrieved dropout imputation model assuming the data are missing not at random (MNAR). At Day 84, the data will be split into two groups as follows: (1) all participants that did not discontinue treatment and had a non-missing value at Day 84; and (2) either participants that had a missing value at Day 84, or participants that had discontinued treatment and had a non-missing value at Day 84. For the second group, 100 data sets will be imputed. The variables for the imputation model will consist of the LDL-C values from Baseline and Day 84, along with treatment group. Each data set will be combined with the first group to obtain 100 imputed data sets with no missing values at Day 84. For each imputation data set, the percent change from Baseline to Day 84 will be analyzed using the ANCOVA model described above. The results of these 100 analyses will be combined to construct the treatment estimates using the parameter estimates and associated standard errors. Similarly, the difference of the adjusted treatment means (obicetrapib vs. placebo) will be presented with the associated standard error and two-sided 95% confidence interval. Randomly chosen seed numbers will be selected for the analysis and will be retained.

Sample SAS code is shown below:

1.1

Note: Missing value imputation only using participant group (2): participants that had a missing value at Day 84, or participants that had discontinued treatment and had a non-missing value at Day 84

TREATMENT = 0 (Placebo), 1 (Obicetrapib)

LDLC_BASE = Baseline LDL_C value

LDLC_Day84 = LDL_C value at Day 84

```
*****  

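### The retrieved-dropout donor rule in SAP 3.4.1 is wider than the SAP's own definition and can admit Day 84 values taken on or close to study drug

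*SAP*

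**What the plan says.** SAP 3.4.1 handles missing Day 84 LDL-C with a retrieved-dropout model. The text explains retrieved dropouts as "participants who remain in the study after treatment discontinuation". The operational step then splits the data in two. Group (1) is participants who did not discontinue and have a Day 84 value. Group (2) is participants with no Day 84 value, together with "participants that had discontinued treatment and had a non-missing value at Day 84". The imputation model is fitted in group (2) alone, on treatment, Baseline and Day 84 LDL-C, and group (1) is merged in afterwards. The note above the sample SAS code repeats the group (2) rule.

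Three other provisions decide who has a Day 84 value:

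- SAP 3.1.2: "Early termination (ET) visits will be assigned to analysis visits according to the following visit windows in Table 2". Table 2 sends Days 58 to 132 to Day 84 and Days 2 to 57 to Day 30. A scheduled visit inside the window takes precedence.
- Protocol 4.3: for those who stop treatment and decline to continue, "an Early Termination (ET) Visit will be scheduled as soon as possible followed by an EOS Visit approximately 35 days later". If the stop happens at an onsite visit, that visit becomes the ET visit.
- Protocol 7.1 measures LDL-C at ET by preparative ultracentrifugation. This is the assay SAP 3.4.1 requires, so a mapped ET value qualifies for the primary analysis.

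**The concern.** The primary estimand uses a treatment-policy strategy. The retrieved-dropout model is there to give participants who stopped and left a Day 84 value like that of people who stopped and were still measured. This works only if the donors were sampled after coming off drug.

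As written, two kinds of donor may not have been. The first is a participant whose only Day 84 value is a mapped ET sample drawn at or shortly after the last dose. The second, if the rule is read literally, is a participant who stopped well after Day 84 and whose Day 84 sample was taken on treatment. Either would pass some of the drug effect to participants with missing data and move the LS mean difference towards obicetrapib. Such donors could also keep the model estimable and so avoid the placebo-based fallback, which SAP 3.4.1 invokes only when convergence or estimation is in doubt.

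**Working it through.** **The plan's own figure.** Protocol 9.2.5: "Assuming an approximate 5% drop out rate, approximately 285 participants will be evaluable for efficacy", with "more than 90% power to detect a 30% reduction of LDL-C (standard deviation 15%) levels" "at a 1-sided significance level of 0.025". 300 × 0.95 = 285, and 2:1 allocation gives 190 and 95. SE = 15 × √(1/190 + 1/95) = 1.885. The planned effect is 30/1.885 = 15.9 standard errors, against 1.96 + 1.28 = 3.24 needed for 90% power. The stated power is reproduced (about 100%).

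**Who is exposed.**

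| Situation | Day 84 value | Donor under group (2) rule? | Donor under prose definition? |
|---|---|---|---|
| Stops before Day 84, stays, sampled at Visit 4 | Visit 4, off drug | Yes | Yes |
| Leaves from Day 58 on without a Visit 4 value, ET by Day 132 | ET sample, time off drug unknown | Yes | No |
| Stops at Visit 4 and leaves | Visit 4, a genuine Day 84 value | Yes | No |
| ET on Days 2 to 57 | Missing (ET goes to Day 30) | No, imputed | No, imputed |
| Stops after Day 84 | Visit 4, on drug | Yes, if read literally | Unclear |

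**Size at 5% stopping.** These inputs are assumptions, not figures in the documents:

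- 200 active participants, on-drug change −30%, off-drug change 0%, and no change in placebo, so that the error in the active mean is the error in the difference;
- 10 active participants stop before Day 84: 4 truly retrieved, 3 with a mapped ET sample fully on drug, 3 missing.

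The steps are:

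- Treatment-policy mean: 190 × (−30)/200 = −28.5.
- Donor mean under the group (2) rule: (3 × (−30) + 4 × 0)/7 = −12.9.
- Resulting active mean: (190 × (−30) + 3 × (−30) + 4 × 0 + 3 × (−12.9))/200 = −29.1.
- Bias through imputation: 3 × 12.9/200 = 0.19. Bias from the ET participants' own values: 3 × 30/200 = 0.45. Total 0.64, or 0.64/1.885 = 0.34 of a standard error.

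At 10% stopping (8, 6 and 6 people) the parts are 6 × 12.9/200 = 0.39 and 6 × 30/200 = 0.90, total 1.29.

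**Later stoppers as donors.** If 10 to 20 on-drug later stoppers join the 4 true donors, the donor mean is (10 × (−30))/14 = −21.4 to (20 × (−30))/24 = −25.0. With 3 missing, the shift is 3 × 21.4/200 = 0.32 to 3 × 25.0/200 = 0.38 points.

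**Simulation of the imputation step.** Set-up: 200 against 100 participants, 8 active donors, 15 or 30 points of effect lost off drug, 400 replicates, 20 imputations, and equal-variance ANCOVA with a normal reference as simplifications. Stopping is heavier than above: 5% missing means 10 missing plus 8 donors, or 18 of 200 active participants. Bias in points, including the ET participants' own values:

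| Share of donors on drug | 5% missing | 10% missing |
|---|---|---|
| None | −0.02 to −0.11 | −0.05 to −0.25 |
| Half | −0.7 to −1.4 | −1.2 to −2.3 |
| All | −1.5 to −2.8 | −2.3 to −4.4 |

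Every replicate stayed significant.

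**The case against.** A reader might infer that any ET sample on Days 58 to 132 becomes the Day 84 value and that dropouts are therefore imputed with on-drug LDL-C. The documents do not support that.

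- A scheduled Visit 4 value takes precedence. Someone sampled at Visit 4 who terminates on Day 110 keeps the Visit 4 value.
- The only scheduled visit inside the window is Visit 4 itself. Other ET samples come from visits arranged as soon as possible, with an unknown lag. A participant who stopped earlier, stayed and later declined is already off drug.
- True retrieved dropouts are donors too, so imputations are a mixture (−12.9% in the illustration, not −30%).
- The prose definition would exclude ET participants, so the SAP is inconsistent rather than settled on including them.
- The split is introduced as being made at Day 84, which may mean discontinuation status on that day. Counting a much later stopper as a donor is a literal reading, not a certain one.

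The illustration is also near the worst case: mapped samples fully on drug, and everyone else fully back to Baseline. The control-based and tipping-point analyses do probe the imputation.

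All of this stands, and it narrows the point. It does not remove it. The rule and its code note carry no date condition and no condition of staying in the study, and they conflict with the definition given in the same section. All three planned sensitivity analyses also keep a mapped ET value as observed Day 84 data, so none of them tests the larger of the two components.

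**Conclusion.** The point holds as an inconsistency in the primary analysis that should be resolved before unblinding. Some donors may carry on-drug or near-on-drug values, and missing values may then be partly imputed with drug effect, in favour of obicetrapib.

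At 5% stopping the illustration gives about 0.2 points from imputation and about 0.6 in total, against a standard error of about 1.9. Both figures rest on the assumed split of stoppers and on 30 points of effect being lost off drug. The documents give neither a half-life nor a time for LDL-C to return after stopping, so the true size cannot be fixed. The larger simulated values need more stopping and a donor pool that is half or wholly on drug.

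A reader might also infer a threat to the trial's conclusion. There is none on the planned effect, which is about 16 standard errors. What is affected is the estimate and its match with the treatment-policy estimand.

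**What to change.** In the group (1)/(2) split of SAP 3.4.1 and in the SAS note:

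1. Define donors as participants who discontinued treatment before their Day 84 sample, remained in the study, and have a Day 84 value from the scheduled visit or from an unscheduled visit used in its place under SAP 3.1.2.
2. Exclude values mapped from ET visits from the donor set.
3. Keep in group (1) participants who continue treatment and those who stop at or after their Day 84 sample.
4. State how mapped ET values enter the primary analysis. If they are kept as observed values, they can be merged after imputation, as group (1) is.
5. Add a sensitivity analysis that treats Day 84 as missing when the only value is an ET sample outside Day 84 ±7.

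In the 5% illustration, items 1 and 2 remove the 0.19 points from imputation. The 0.45 from ET participants' own values remains if those values are kept, and item 5 shows how much it matters. Dropping such samples from the primary analysis would replace observed values with imputed ones, a trade-off better left to the sensitivity analysis. A minimum time off drug cannot be set from the documents.

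The cost is SAP wording and code, with no added visits or samples. The donor pool shrinks (from 7 to 4 in the illustration), which makes the imputations less precise and the fallback more likely. The placebo-based fallback for that case is already specified.

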- A $>25\%$ decrease in eGFR from Baseline or an eGFR < 30 mL/min/1.73 m², calculated using the Chronic Kidney Disease Epidemiology Collaboration equation, and/or an increase in serum creatinine of ≥ 0.3 mg/dL (≥ 26.5 μ mol/L) from Baseline;
- Changes to antihypertensive medication(s) due to changes in blood pressure in those participants receiving antihypertensive medication(s) treatment at Baseline and those participants not receiving antihypertensive medication(s) treatment at Baseline; and
- Macular degeneration.

An overview of ESIs described above will be provided including counts, percentages of participants by treatment group, and a listing of each ESI.

Values and changes from baseline will be summarized for ALT, AST, and total bilirubin by visit and treatment group. The number and percent of participants with abnormal values for ALT, AST, and total bilirubin will be summarized. These summaries of participants with abnormal values will be performed overall; by normal Baseline; and by abnormal Baseline for ALT, AST, and total bilirubin individually. Hy's Law criteria ($>3 \times \text{ULN}$ for either ALT or AST, with accompanying total bilirubin $>2 \times \text{ULN}$) will also be applied to the data. Any potential Hy's Law cases will be listed separately.

Values and changes from Baseline will be summarized for CK levels by visit and treatment group and visit. In addition, the number and percent of participants with abnormal CK values will be summarized. These summaries of participants with abnormal CK values will be performed overall, by normal Baseline CK, and by abnormal Baseline CK. Values of CK from Baseline to EOT will be summarized by treatment group and by Baseline eGFR category.

Cases of NODM will be recorded and summarized using the appropriate system organ class. These events will be summarized by severity and relationship to study drug for each treatment group. Fasting plasma glucose and HbA1c will be monitored as specified in [Table 1 Schedule of Procedures](#).

Baseline eGFR will be summarized by treatment group for actual value and for Baseline eGFR categories. Shift tables of eGFR category from Baseline to EOT will be provided by treatment group. Shift tables of urine albumin-creatinine ratio and urine protein-creatinine ratio from Baseline to EOT will be provided by treatment group.

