Participants will be identified as those who had a diagnosis of hypertension in their medical history and received antihypertensive medication(s) at Baseline. If participants had an adverse event related to hypertension after Baseline (see [Appendix B](#) for preferred terms) and had any change in antihypertension medication within 30 days of the start date of the adverse event, that change

in antihypertension medication will be considered as due to a change in blood pressure. The number and percentage of participants will be summarized by treatment group.

Participants will be identified who did not have a prior diagnosis of hypertension in their medical history and did not receive antihypertensive medication(s) at Baseline. If participants had an adverse event of hypertension and initiated antihypertension medication within 30 days of the start date of the adverse event, the adverse event will be classified as a change in blood pressure. The number and percentage of participants will be summarized by treatment group.

Cases of macular degeneration will be recorded and summarized using the appropriate system organ class. These events will be summarized by severity and relationship to study drug for each treatment group.

3.5.3 *Clinical Laboratory Tests*

Blood and urine samples for clinical laboratory evaluations (including a full serum chemistry panel, hematology, coagulation, and urine dipstick analysis) will be collected at visits specified in [Table 1](#). A limited serum chemistry panel will also be collected as specified in Table 1. All safety laboratory samples should be collected while the participant is fasting (a minimum of 8 hours) and prior to the next dose of study drug (at applicable visits). Urinalysis will be performed locally by dipstick analysis from a sample of mid-stream urine. See clinical protocol ([Appendix B](#)) for a complete list of analytes.

Laboratory values will be summarized descriptively, including the change from Baseline. In addition, shift tables for all parameters will be presented to describe the change in laboratory parameter values at end of treatment visit using normal range categories (low, normal, and high).

Chemistry and hematology laboratory parameters will be listed.

3.5.4 *Vital Signs*

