Vital signs (heart rate and blood pressure) measured in triplicate prior to study administration at applicable visits as indicated in Table 1. Values will be summarized with descriptive statistics, including the change from Baseline at each visit by treatment group and overall.

Additional summaries of blood pressure measurements will be performed, within treatment group and time point, using counts of triplicate means that meet the following criteria:

- Systolic blood pressure:
 - ≥ 160 mmHg
 - ≥ 180 mmHg
 - change from Baseline by ≥ 20 mmHg
- Diastolic blood pressure:
 - ≥ 100 mmHg
 - ≥ 110 mmHg
 - change from Baseline by ≥ 15 mmHg.

As described above, the number and percentage of participants receiving antihypertensive medications at Baseline with changes to antihypertensive medications due to change in blood pressure will be summarized by treatment group. The number of participants who were not hypertensive or on any antihypertensive medications at Baseline, but started one or more antihypertensive drugs during the treatment period, will be summarized by treatment group.

Vital signs will be listed.

3.5.5 *Electrocardiograms*

A single 12-lead ECG will be performed at Visit 2 and Visit 7/EOT/ET and will be read locally.

ECG parameters will be recorded as normal, abnormal or not done. Abnormal values will be assessed as clinically significant or not clinically significant. Counts and percentages for ECG parameters will be summarized by treatment group and in total.

3.5.6 *Physical Examinations*

Physical examinations (with focused examination on general, respiratory, CV, abdominal, and extremities evaluations) and recording of weight and height will be performed at Screening Visit and Visit 7/EOT/ET. Height will be measured at Screening Visit only and used to calculate body mass index. BMI will be calculated as weight/(height/100)² (kg/m²); rounded and displayed to 1 decimal place.

Physical examination, parameters, will be recorded as normal, abnormal or not done. Abnormal values will be assessed as clinically significant or not clinically significant. Count and percentages for physical parameters will be summarized by treatment group and in total.

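### Table 2 of the SAP counts an Early Termination visit as EOT only from Day 318, so the Baseline-to-EOT safety tables have no record for participants who leave earlier

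*SAP*

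**What the plan says.** **Assignment of ET visits.** SAP 3.1.2, under General Considerations and not limited to lipids, says: "Early termination (ET) visits will be assigned to analysis visits according to the following visit windows in Table 2". The windows are Days 2–57 (Day 30), 58–132 (Day 84), 133–225 (Day 180), 226–317 (Day 270), and Day 318 onward with no upper limit for the row that Table 2 labels as both EOT and Visit 7.

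**Precedence.** The same section says that "if a scheduled visit occurs within the analysis day window, then the measurement from this scheduled visit will be used". The fallback that follows deals with unscheduled measurements. ET visits are not mentioned in either rule.

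**Outputs defined to EOT.** SAP 3.5.2: "Shift tables of eGFR category from Baseline to EOT will be provided by treatment group". The same section plans UACR and UPCR shift tables to EOT, and CK to EOT by Baseline eGFR category. SAP 3.5.3: "shift tables for all parameters will be presented to describe the change in laboratory parameter values at end of treatment visit". Protocol 9.2.2 planned the laboratory shift tables at post-Baseline visits in general.

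**What an ET visit is.** Protocol 4.3: "The ET Visit procedures are identical to the End of Treatment (EOT) Visit procedures". The schedules in both documents have a single column for Visit 7, EOT and ET. An ET visit applies to participants who stop treatment and decline to continue. Those who stop drug but stay keep their scheduled visits.

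**The concern.** The protocol designs the ET visit as the end-of-treatment assessment of a participant who leaves. Table 2 relabels that assessment as Day 30, 84, 180 or 270 unless it happens on Day 318 or later, and no other rule in the SAP returns it to EOT. The safety tables that look only at EOT would then leave out early leavers, although the Safety Population is everyone who took a dose. Some of these people may have left for tolerability, so the tables could be selectively incomplete, and not necessarily to the same degree in each arm.

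The SAP's move from laboratory shifts at post-Baseline visits to a shift at the end-of-treatment visit makes this worse. Under the protocol's version an early leaver would still appear in the shift tables for the visits attended. SAP Section 6 lists four changes from the protocol, and this is not among them.

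**Working it through.** **1. The plan's own figures.** Planned enrollment is about 300 with about 5% drop-out (SAP 2.2.2): 300 × 0.95 = 285 evaluable, as stated, which leaves 300 − 285 = 15. The Table 2 cut-points are the midpoints between target days: (30+84)/2 = 57, (84+180)/2 = 132, (180+270)/2 = 225, (270+365)/2 = 317.5. The table is internally consistent; the issue is what it is applied to.

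**2. Days on which an ET visit is not EOT.** Window lengths are 56 (Days 2–57), 75 (58–132), 93 (133–225) and 92 (226–317). Sum: 56 + 75 + 93 + 92 = 316 days. An ET visit on any of these has no EOT label. This needs no assumption about timing. It also holds when the participant stops at a scheduled onsite visit: a Visit 5 on Day 180 that becomes the ET visit is still mapped to Day 180.

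**3. How many participants.** The documents give neither the number of ET visits nor their timing. Assume that all 15 drop-outs have an ET visit, spread evenly over Days 2–364 (363 days):

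- share before Day 318 = 316/363 = 0.871
- participants without an EOT record = 15 × 0.871 = 13.1, about 13
- with equal drop-out in the two arms at 2:1, 13.1 × 2/3 = 8.7 on obicetrapib and 13.1 × 1/3 = 4.4 on placebo.

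For these 15 the range is 0 (no ET visit before Day 318) to 15 (all before Day 318). The 5% refers to evaluability for efficacy and is not a one-year ET rate. On the same even-timing assumption, each percentage point of participants with an ET visit is 3 people, of whom 3 × 0.871 = 2.6 would lack an EOT record.

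**4. The tie within a window.** Example: Visit 4 on Day 84 and an ET visit on Day 110 both fall in Days 58–132. One reading takes the Visit 4 value under the precedence sentence. Another treats the ET visit as a scheduled visit, because the schedule gives it a column with Visit 7. The text does not choose. With scheduled visits on target, a tie is possible on (57−30) + (132−84) + (225−180) + (317−270) = 27 + 48 + 45 + 47 = 167 of 316 days. Whether the ET value is lost on those days depends on a rule that is not written.

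**The case against.** **EOT need not mean the Table 2 row.** The safety sections do not cite Table 2 or Day 318, and the protocol equates ET procedures with EOT procedures, so a programmer might take EOT to include ET. That is a fair statement of the probable intent. But Table 2 is the only place where the SAP attaches EOT to an analysis visit, and its rule for ET visits is explicit and general. The objection supports writing the intent down.

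**A fixed-time table is a legitimate choice.** Windowing by day keeps exposure comparable within a column. This stands for the by-visit tables, which is why the windowing should remain there. It does not explain why tables headed to EOT should omit the visit designed as the end-of-treatment assessment.

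**Exit values survive elsewhere.** This stands. AE summaries, ESI counts, counts of abnormal ALT, AST, bilirubin and CK, the Hy's Law listing, and the chemistry and hematology listings do not depend on the EOT label. All safety analysis is descriptive.

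**Stronger readings that a reader might infer.**

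- *Scheduled visits override ET values, so about half of exit values disappear from by-visit tables.* The SAP does not rank the two. The 167/316 = 52.8% also needs even ET timing, visits on target, no ET visit that is itself a scheduled visit, and an analyte sampled at every visit. If half of ET visits were themselves scheduled visits, it is 52.8% × 0.5 = 26.4%; with every scheduled visit at the early edge of its window, 191/316 = 60.4%. For parameters with one interim sample at Visit 5 it is 45/316 = 14.2%, and for ECG it is zero.
- *All 15 drop-outs vanish.* That follows only if every ET visit is assumed to fall before Day 318.
- *Exit ECGs are lost.* SAP 3.5.5 says "A single 12-lead ECG will be performed at Visit 2 and Visit 7/EOT/ET and will be read locally". It plans counts and percentages, not a table restricted to the Table 2 EOT row, and no interim ECG competes.

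**Conclusion.** The point holds for the outputs defined to EOT. As written, the eGFR, UACR/UPCR and CK outputs to EOT and the laboratory shift tables contain no post-Baseline record for a participant whose ET visit is before Day 318. They describe people with a value at Day 318 or later. This rests on taking Table 2 as the meaning of EOT, the only meaning the SAP supplies.

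The size is small in headcount: about 13 of 300 under the even-timing and 5% assumptions, neither of which the documents establish for ET visits. Participants who stop drug but stay can still have a Day 365 value. No efficacy or power figure changes.

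Two lesser gaps accompany it: ET-versus-scheduled precedence is unspecified, and the narrowing of the laboratory shift tables is not declared in SAP Section 6. The documents do not support a claim that half of exit values are discarded, or that safety signals in leavers would go unreported. This is a cheap improvement to make before database lock.

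**What to change.** 1. Keep Table 2 windowing for the by-visit tables. Confining it to lipids would remove ET safety values from by-visit tables that they now fill.
2. Add to SAP 3.1.2 that, for every safety output defined to EOT, the EOT record is the Visit 7/EOT/ET visit on whatever day it occurs, carried by a separate analysis flag.
3. State in SAP 3.1.2 which value is used when an ET visit and an attended scheduled visit fall in the same window.
4. In SAP 3.5.3, restore the laboratory shift tables at post-Baseline visits, or list the narrowing in SAP Section 6 with its reason.

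The cost is a few sentences and one flag. The downside is that the EOT column will mix exposure lengths; a footnote can say so.
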